Nanoliposomal irinotecan will be administered by IV infusion over approximately 90 minutes. One cycle is 14 days, subsequent doses should be administered on the first day of each cycle +/- 3 days. An additional 1 day is provided for a holiday.

Three patients will be accrued to level 1. If no dose limiting toxicities are observed following completion of 4 weeks (2 cycles) of treatment then accrual to dose level 2 will proceed (patients must be evaluated prior to their cycle 3 treatment and this will be used to confirm DLTs). If a DLT is observed in one of the first 3 patients in a dose level, then accrual for that level will be expanded to 6 patients. Accrual will continue in this way until the MTD of nanoliposomal irinotecan with temozolomide 50mg/m²/day is determined. Two or more instances of DLT in a cohort of 6 patients will result in the preceding dose level being defined as the MTD. If two or more instances of DLT in a cohort of 6 patients occurs in dose level 1 then dose level -1 of nanoliposomal irinotecan will be investigated. After determination of the MTD, the final cohort will be expanded so that a total of 25 patients are treated on study. The final cohort will be treated at the MTD.

If a patient is unable to receive 4 weeks of treatment (2 cycles) for reasons other than dose limiting toxicity, they will be replaced in a cohort.

Premedication

All patients must be premedicated prior to nanoliposomal irinotecan infusion with standard doses of dexamethasone and a 5-HT3 antagonist or other anti-emetics as per standard institutional practices for irinotecan administration. Atropine may be prescribed prophylactically for patients who experienced acute cholinergic symptoms in previous cycles.

Premedication prior to temozolomide is not required and may be administered as per institutional standard of care.

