5.1 Treatment Delay

A new course of treatment (cycle) with nanoliposomal irinotecan and temozolomide should not begin until the following criteria are met.

- Platelets $\geq 100,000 \times 10^9/L$ (100,000/mm³)
- Granulocytes (ANC) $\geq 1.5 \times 10^9/L$ (1,500/mm³)
- Recovery from other clinically significant, treatment related non-hematologic toxicities to \leq Grade 2

*please refer to section 5.2 for events that require dose reductions cycles 3-on*The treating physician may decide to hold treatment secondary to other toxicities even if deemed not related to treatment if the physician feels it is in the patient's best interest. This must be documented and submitted to BrUOG on treatment form and AE log.

If the patient does not meet these criteria at the start of a scheduled cycle, treatment should be delayed until these requirements are met.

Patients who require a treatment delay of more than 4 weeks due to toxicity will be removed from protocol treatment. Patients who require a treatment delay of more than 8 weeks not due to toxicity will be removed from protocol treatment.

If a patient is unable to receive 4 weeks of treatment (2 cycles) for reasons other than a dose limiting toxicity, they will be replaced in a cohort.

5.2 Definition of Dose Limiting Toxicities:

Dose limiting toxicities will be defined as the following toxicities occurring during the first 2 cycles (28 days) of therapies. If however a patient experiences one of the below toxicities after cycle 2 they will be dose reduced (both drugs), even though it will no longer be defined as a DLT.

- Grade 4 neutropenia (ANC < 500/mm³) for > 7 days
- ANC < 1000/mm³ with fever or infection
- Platelets < 25,000/mm³
- Platelets < 50,000/mm³ requiring transfusion
- Grade 3 or 4 treatment related non-hematologic toxicities excluding alopecia.
 - Grade 3 nausea, vomiting or diarrhea will only be considered a dose limiting toxicity if it occurs for greater than 72 hours despite maximal medical support.
 - Grade 3 electrolyte abnormalities will not be considered dose limiting toxicities if the electrolyte disorder can be corrected to grade 2 or less within 72 hours.
 - A grade 4 electrolyte abnormality will be considered a DLT.
- Delay of treatment for > 2 weeks due to toxicity (do not score a second DLT for a treatment delay caused by the same event)

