Late diarrhea (generally occurring more than 24 hours after administration of irinotecan) can be life threatening since it may be prolonged and may lead to dehydration, electrolyte imbalance, or sepsis. Late diarrhea should be treated promptly with loperamide, and octreotide should be considered if diarrhea persists after loperamide. Loss of fluids and electrolytes associated with persistent or severe diarrhea can result in life threatening dehydration, renal insufficiency, and electrolyte imbalances, and may contribute to cardiovascular morbidity. The risk of infectious complications is increased, which can lead to sepsis in patients with chemotherapy-induced neutropenia. Patients with diarrhea should be carefully monitored, given fluid and electrolyte replacement if they become dehydrated, and given antibiotic support if they develop ileus, fever, or severe neutropenia as per institutional standard practice

Neutropenia

Deaths due to sepsis following severe neutropenia have been reported in patients treated with irinotecan. Neutropenic complications should be managed promptly with antibiotic support. Patients, who are known to have experienced Grade 3 or 4 neutropenia while receiving prior anti-neoplastic therapy, should be monitored carefully and managed as outlined in the section on dose modifications and as per institutional standard practice.

Hypersensitivity

Hypersensitivity reactions including severe anaphylactic or anaphylactoid reactions have been observed. Suspected drugs should be withheld immediately and aggressive therapy should be given if hypersensitivity reactions or infusion reactions occur as outlined in section 5.4 .

Colitis/Ileus

Cases of colitis complicated by ulceration, bleeding, ileus, and infection have been observed. Patients experiencing ileus should receive prompt antibiotic support as per institutional standard practice.

Thromboembolism

Thromboembolic events have been observed in patients receiving irinotecan- containing regimens; the specific cause of these events has not been determined.

Pregnancy

The pregnancy category of irinotecan is D. Women of childbearing potential should be advised to avoid becoming pregnant while receiving treatment with irinotecan. If a pregnancy is reported, treatment should be discontinued. The patient should be withdrawn from the study, and the pregnancy should be followed until the outcome becomes known as per SAE section.

Care of Intravenous Site

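### A treatment-related death in the first 28 days that meets no other listed item is not a DLT as written, and the replacement rule then drops that patient from the cohort

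*Combined protocol and SAP*

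**What the plan says.** Section 5.2 introduces a closed list: "Dose limiting toxicities will be defined as the following toxicities occurring during the first 2 cycles (28 days) of therapies". The only item for non-hematologic events is "Grade 3 or 4 treatment related non-hematologic toxicities excluding alopecia", followed by qualifiers for gastrointestinal and electrolyte events. The list in section 17.0 words this item the same way. Neither list mentions grade 5 or death.

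The cohort rules are in section 4.0 and are repeated in section 17.0. For expansion: "If a DLT is observed in one of the first 3 patients in a dose level, then accrual for that level will be expanded"; the enlarged cohort has 6. For the MTD: "Two or more instances of DLT in a cohort of 6 patients will result in the preceding dose level being defined as the MTD".

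The replacement rule appears in sections 4.0, 5.1 and 17.0. In section 4.0 it covers a patient "unable to receive 4 weeks of treatment (2 cycles) for reasons other than dose limiting toxicity, they will be replaced in a cohort". None of the three clauses makes an exception for a patient who dies of toxicity.

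Elsewhere, death appears in the SAE definition (11.1), under recording (11.2), under reporting (11.3.3 and 11.6), and as a reason for removal from therapy (12.0, item 10). None of these sections connects it to the DLT count.

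**The concern.** The MTD is the first primary objective (1.1.1), and it rests wholly on the DLT count. The non-hematologic item stops at grade 4, so the most severe outcome is not named. A patient who dies cannot complete two cycles. If the death is not a DLT, the replacement clause applies, and the patient leaves both the numerator and the denominator. Escalation, or the declaration of a level as tolerable, could then follow a drug-related death that the count does not show.

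**Working it through.** The plan gives no operating characteristics for the escalation part, so there is no printed figure to reproduce. The check is a reading of the text, followed by the cohort arithmetic.

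**1. Which related deaths are already DLTs?**
- ANC below 1000/mm³ with fever or infection: counted, in both lists.
- Platelets below 25,000/mm³, or below 50,000/mm³ requiring transfusion: counted.
- Neutropenia below 500/mm³: counted, in 5.2 only if it lasts more than 7 days.
- A related grade 3-4 event that met the item and was recorded before death: counted, because it occurred in the window.

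**2. Which are not?** Related deaths in the first 28 days that meet none of the above. The plan's own terms leave room for them:
- Section 6.0 schedules blood counts only within 3 days before day 1 of each 14-day cycle, so a mid-cycle death may have no ANC on record.
- Grade 3 nausea, vomiting or diarrhea counts only after more than 72 hours despite maximal support. A patient who dies sooner, with no recorded grade 4 phase, meets no item.
- The item on treatment delay of more than 2 weeks does not naturally describe a patient who has died.

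**3. Cohort of 3: one uncaught related death, two clean patients.** Let g be the chance that a further evaluable patient has a listed DLT (assumed).
- Counted: 1/3, expand to 6. Escalation needs no DLT in the next three: (1 − g)³ = 0.729 at g = 0.10 and 0.512 at g = 0.20.
- As written: replace the patient. A clean replacement permits immediate escalation, with probability 1 − g = 0.90 or 0.80. If the replacement has a DLT, the level expands and may still clear. In total (1 − g) + g(1 − g)³ = 0.9 + 0.1 × 0.729 = 0.973, or 0.8 + 0.2 × 0.512 = 0.902.

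**4. Level of 6: one uncaught related death, one listed DLT, four clean patients.**
- Counted: 2/6, so the preceding level is the MTD.
- As written: replace the patient. If the replacement is DLT-free (probability 1 − g), the result is 1/6 and the level is cleared. If not, it is 2/6.

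**5. Before any data.** Let g be the rate of listed DLTs and q the rate of related deaths meeting no listed item, with no overlap. With per-patient rate p,

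P(escalate) = (1 − p)³ + 3p(1 − p)² × (1 − p)³.

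If deaths count, p = g + q. If they are uncounted and replaced, p = g/(1 − q). For g = 0.20 and q = 0.05:
- counted, p = 0.25: 0.4219 + 0.1780 = 0.600
- as written, p = 0.20/0.95 = 0.2105: 0.4921 + 0.1937 = 0.686

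| g | q | counted | as written |
|---|---|---|---|
| 0.10 | 0.05 | 0.814 | 0.897 |
| 0.20 | 0.02 | 0.665 | 0.700 |
| 0.20 | 0.05 | 0.600 | 0.686 |
| 0.20 | 0.10 | 0.494 | 0.660 |

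Over g from 0.10 to 0.30 and q from 0.02 to 0.10, the literal text raises P(escalate) by about 3 to 18 percentage points.

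**The case against.** **Most toxic deaths may already be caught.** A reader might infer that every treatment-related death escapes the count. The documents do not support that. The hematologic items have no upper limit of severity, and a fatal event with a recorded qualifying grade 3-4 phase is a DLT on the plain text. Section 5.4 places life-threatening infusion reactions at grade 4, so a reaction graded there before death would count. This stands, and it confines the gap to step 2 of the working.

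**The plan's own warning about deaths concerns a caught event.** Section 9.1.5 says "Deaths due to sepsis following severe neutropenia have been reported in patients treated with irinotecan". It is tempting to cite this as an example of the gap, but such a death would normally meet the ANC item. The same section calls late diarrhea potentially life threatening without reporting deaths from it. The documents report no death of the kind that escapes.

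**Grade 5 is not defined in the documents.** They cite CTCAE 4.03 without printing its scale. That a fatal event is scored above grade 4 is therefore an assumption here. Without it, the lists are still silent on death.

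**Other safeguards exist.** Related deaths are reported within 24 hours (11.3.3, 11.6), the DSMB reviews adverse events and can meet when needed (16.0), and unacceptable risk can close the study (15.6). It would be wrong to infer that nothing stands between such a death and escalation. But none of these sections changes the DLT count, and the DSMB's routine meetings are twice a year.

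**Anyone would count a toxic death.** That is very likely the intent. It is a reason to write it down, since the cohort decision should not depend on investigators departing from the text.

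**Conclusion.** The gap is real but narrow. It covers treatment-related deaths in the first 28 days that meet no other listed item. For those patients, following the text exactly gives a wrong count for the first primary objective.

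At a six-patient level with one other DLT, counting the death makes the preceding level the MTD, whereas the literal text clears the level if the replacement is DLT-free. In a cohort of 3 the difference is between expansion and a single replacement. A reader might infer that the final decision always reverses, but expansion can still end in escalation, as step 3 shows.

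The conclusion rests on the wording alone. The probabilities are illustrations: g and q are assumed, and no figure in the documents supports a particular rate of uncaught related deaths.

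**What to change.** In sections 5.2 and 17.0, extend the non-hematologic item so that it includes treatment-related grade 5 events, for example *Grade 3 or higher treatment-related non-hematologic toxicities*, keeping the alopecia exclusion and the existing qualifiers. Keep the current treatment-related standard. A broader rule that counts any death not clearly due to progression would shift the burden of attribution; that is debatable in recurrent glioblastoma and is not needed to close the gap.

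In sections 4.0, 5.1 and 17.0, reconcile the replacement clauses so that a patient who dies of treatment-related toxicity in the DLT window stays in the cohort count and is not replaced.

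The cost is one line in two lists and one clause in three places, by amendment. The planned total of 25 patients and the study procedures do not change. The downside is that the selected dose level may be slightly lower.

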5.3 Dose Modifications

Dose limiting toxicities are defined in the first two cycles of treatment. Patients experiencing a toxicity defined above in section 5.2 at any time on protocol treatment, will have a 1 dose level reduction of nanoliposomal irinotecan **and** temozolomide. Patients experiencing a second dose limiting toxicity will be removed from protocol treatment.

For patients whose treatment is held for grade 3 or 4 non-hematologic adverse events not related to treatment (which would be at treating physician's discretion and not required per study), dose reductions are not required when treatment is resumed.

Patients can resume treatment once they have recovered from other clinically significant, treatment related non-hematologic toxicities to \leq Grade 2, their platelets count is $\geq 100,000 \times 10^9/L$ (100,000/mm 3) and their ANC count is $\geq 1.5 \times 10^9/L$ (1,500/mm 3). Patients can resume treatment post a dose limiting toxicity (with a dose level reduction to both drugs), once they have recovered from treatment related non-hematologic toxicities to \leq grade 2 and their platelets count is $\geq 100,000 \times 10^9/L$ (100,000/mm 3) and their ANC count is $\geq 1.5 \times 10^9/L$ (1,500/mm 3). A patient is required to be removed from protocol treatment if treatment is held in cycles 1 or 2 for a DLT >4 weeks. Patient's removed from treatment for this reason would undergo off study assessments, followed by 30 day assessments and would be followed as per section 6.

If a patient experiences an event outlined in 5.2 after cycle 2, they will need to be dose reduced (both drugs), even though it will no longer be defined as a DLT.

Treatment:

Nanoliposomal irinotecan 1 cycle = 14 days

	Dose Level -1	Dose Level 1	Dose Level 2	Dose Level 3
Nanoliposomal irinotecan	43 mg/m 2 , day 1	50 mg/m 2 , day 1	70 mg/m 2 , day 1	80 mg/m 2 , day 1

Temozolomide: Daily x 14 days = 1 cycle

	Dose Level -1	Dose Level 1 (Starting dose level all)
Temozolomide	25mg/m 2 /day	50mg/m 2 /day

Patients who require more than one dose reduction will be removed from protocol treatment.

5.4 Management of nanoliposomal irinotecan Infusion Reactions

Infusion reactions will be defined according to the National Cancer Institute CTCAE (Version 4.03)

Grade 1: Mild transient reaction; infusion interruption not indicated; intervention not indicated

Grade 2: Therapy or infusion interruption indicated but responds promptly to symptomatic treatment (e.g., antihistamines, NSAIDS, narcotics, IV fluids); prophylactic

7/21/16, 7/26/16, 8/1/16, 8/2/16, 8/3/16, 8/4/16, 8/9/16, 8/15/16, 8/16/16, 8/17/16 submitted Merrimack, 10/3/16 Merrimack edits, 10/7/16. 10
Re-submitted Merrimack 10/11/16, 11/15/16 from Merrimack, 11/17/16, 11/30/16 back to Merrimack, approved Merrimack 1/5/17,
1/26/17, 2/7/17 company review, 2/8/17, 2/13/17, 3/2/17 company, 3/3/17, approved company 3/23/17, RN/Pharmacy/EXEC review
3/31/17, 3/31/17 BrUOG, to company 4/6/17, Ipsen 4/18/17, BrUOG 4/20/17, Ipsen approved 5-4-17, FDA 5-5-17, FDA IND exemption
5/18/17, Protocol change 5/18/17, Protocol change 7/10/17 with IB v10, 8/17/17, Amendment # 1 4/6/18, Amendment #2 8/14/18,
Amendment # 3 12/8/18

medications indicated for <=24 hrs

Grade 3: Prolonged (e.g., not rapidly responsive to symptomatic medication and/or brief interruption of infusion); recurrence of symptoms following initial improvement; hospitalization indicated for clinical sequelae

Grade 4: Life-threatening consequences; urgent intervention indicated

Study site policies or the following treatment guidelines may be used (not required) for the management of infusion reactions.

Grade 1

- Slow infusion rate by 50%
- Monitor patient every 15 minutes for worsening of condition

Grade 2

- Stop infusion
- Administer diphenhydramine hydrochloride 50 mg IV, acetaminophen 650 mg orally, and oxygen
- Resume infusion at 50% of the prior rate once infusion reaction has resolved
- Monitor patient every 15 minutes for worsening of condition
- For all subsequent infusions, consider premedicating with diphenhydramine hydrochloride 25-50 mg IV

For patients who experience a Grade 1 or Grade 2 infusion reaction, future infusions may be administered at a reduced rate (over 120 minutes), at the discretion of the Investigator.

For patients who experience a second grade 1 or 2 infusion reaction, it is suggested but not required that you administer dexamethasone 10 mg IV. It is suggested that subsequent infusions should be premedicated with diphenhydramine hydrochloride 50 mg IV, dexamethasone 10 mg IV, and acetaminophen 650 mg orally.

Grade 3

- Stop infusion and disconnect infusion tubing from patient
- Administer diphenhydramine hydrochloride 50 mg IV, dexamethasone 10 mg IV, bronchodilators for bronchospasm, and other medications or oxygen as medically necessary
- No further treatment with nanoliposomal irinotecan will be permitted

Grade 4

- Stop the infusion and disconnect infusion tubing from patient
- Administer epinephrine, bronchodilators or oxygen as indicated for bronchospasm
- Administer diphenhydramine hydrochloride 50 mg IV, dexamethasone 10 mg IV
- Consider hospital admission for observation

- No further treatment with nanoliposomal irinotecan will be permitted

See section 9.1.5 for Toxicity Considerations with nanoliposomal irinotecan

6.0 SCHEDULE OF EVALUATIONS / STUDY CALENDAR* The day an assessment (PE, labs, scan etc) is completed is day 0 for counting for example labs drawn on Friday can be used for Monday dosing as this is within 3 days*

Parameter	Pre-study (to be sent to BrUOG prior to registration)	Within 3days prior to Day 1 of Each Cycle (Every 2 weeks) ^C	Every 2 months during treatment	Off study (post completion of final cycle)+ 1 week	30 days post last dose of drug (+1 week)	FU ^D
Informed Consent (within 30 days of day 1) *pts are to be re-consented if ICF will be outside 30 day window	X					
History , Demographics (baseline only)	X					
Concomitant medication log	X	X		X		
Physical examination	X	X	X	X	X ^G	X
Weight	X	X	X	X		
Vital signs	X	X	X	X		
Toxicity Assessment	X	X	X	X	XF	
Performance Status	X	X	X	X	X ^G	
CBC, diff, platelet count	X (within 14 days)	X		X		
Na, K, BUN, Cr	X (within 14 days)	X				
AST, ALT, Bili, Albumin	X (within 14 days)	X				
Serum Pregnancy ^E	X (within 7 days of drug)					
MRI brain with contrast	X ^A (within 28 days)		XH	X (not required for patients who had an MRI completed in prior 2 months)		X
EKG ^B	X					

Survival and Disease status			X		X	X
-----------------------------	--	--	---	--	---	---

^A- Brain MRI with contrast for disease assessment should be performed within 28 days of study entry. Each time: Report required to be sent to BrUOG.

^B- EKG within 8 weeks of study entry. Report required.

^C It is appropriate to use labs from screening for cycle 1 day 1, if labs are within 14 days (pregnancy must be within 7 days of drug day 1 as noted above for applicable patients). A physical exam within 7 days prior to cycle 1 day 1 may be utilized. Weight, vitals, PS, AE and conmed assessment can be used from screening for cycle 1 day 1 if within 14 days. Labs and physical exam (with weight, vitals, PS and AEs) for all subsequent cycles can be within 3 days prior to day 1 of treatment cycle (another 1 day is given for holiday).

^D- For patients removed from protocol treatment due to toxicity(or other reason), without progression, follow-up until disease progression will include brain MRI, disease free and overall survival and physical approximately every 3 months (+/- 1 month). For patients who come off study for progression, overall survival is to be reported approximately every 3months (+/- 1 month). Follow-up will be for 2 years.

^E post-menopausal women (surgical menopause or lack of menses \geq 12 months) do not need to have a pregnancy test, document status

^F Adverse event evaluation, inclusive of SAE evaluation, and Performance status assessment will be done 30 days (+1 week) post last dose of drug . SAEs occurring outside this 30 day window must be reported if the event is considered to be possibly related to the study drug. If a patient begins a new treatment, AE evaluation will be stopped unless the patient experiences an event that is thought to be possibly related to the study drug. SAE evaluation will not be stopped if patient begins a new treatment.

^G Physical and performance status assessment to be done in coordination with 30 day toxicity assessment (+ 1 week allowed).

^H MRI of brain with contrast to be done every 2 months (approximately after every 4 cycles) +1 month window.. More frequent MRI imaging is allowed per treating MD but all information must be sent to BrUOG.

7.0 RESPONSE ASSESSMENT:

7.1 Response Definition:

Response and progression will be evaluated in this study using standard criteria for patients with malignant gliomas. A major difference in response criteria for patients with brain tumors from measuring response in other solid tumors is the requirement that patients be on a stable or decreasing dose of corticosteroids when evaluating for response because of the potentially confounding impact of corticosteroids on contrast enhancement during brain tumor imaging. The tumor size will be measured in millimeters and is the largest cross-sectional area using perpendicular measurements of contrast enhancing abnormality.

Complete Response (CR): Complete disappearance of all enhancing tumor on MRI scans while, off corticosteroids, and neurologically stable or improved.

Partial Response (PR): \geq 50% decrease in size of enhancing tumor on MRI scans, corticosteroids stable or reduced, and neurologically stable or improved.

Stable Disease (SD): Does not qualify for CR, PR, or PD.

Progression: \geq 25% increase in the size of enhancing tumor or any new tumor; or neurologically worse, and steroids stable or increased.

Best Radiographic Response: The best response will be defined as the best radiographic response (CR, PR, SD, or PD) for patients evaluable for radiographic response while on study.

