Patients can resume treatment post a dose limiting toxicity (with a dose level reduction to both drugs), once they have recovered from treatment related non-hematologic toxicities to \leq grade 2 and their platelets count is $\geq 100,000 \times 10^9/L$ (100,000/mm³) and their ANC count is $\geq 1.5 \times 10^9/L$ (1,500/mm³). A patient is required to be removed from protocol treatment if treatment is held in cycles 1 or 2 for a DLT > 4 weeks. Patient's removed from treatment for this reason would undergo off study assessments, followed by 30 day assessments and would be followed as per section 6.

Of note when a patient experiences a DLT both drugs must be held and then both must be reduced, but they may be reduced at different times if a patient is found to experience a DLT mid-cycle. If this occurs, the TMZ will be held until patient's toxicities resolve to criteria above, after-which the dose of TMZ will be reduced for the remainder of the cycle and then at the start of the next cycle the nanoliposomal irinotecan will be reduced.

Example 1: If prior to day 1 of a cycle a patient experiences a DLT, dosing will be held until criteria for treatment are met. Both drugs will then be reduced.

Example 2: If a patient meets dosing criteria day 1 the cycle will begin and patient will be treated day 1 with both drugs. Since TMZ is given on a continuous basis if a patient experiences a DLT on day 5 TMZ will be held until patient meets criteria for treatment and then TMZ will be dose reduced for the remainder of the cycle. Nanoliposomal irinotecan will be dose reduced at the next cycle.

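### After a grade 3–4 infusion reaction, section 5.4 stops nanoliposomal irinotecan (in a list marked optional) while sections 5.2–5.3 require reduction and allow resumption

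*Combined protocol and SAP*

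**What the plan says.** Section 5.4 defines infusion reactions by CTCAE grade and lists management steps for each. The list opens: "Study site policies or the following treatment guidelines may be used (not required) for the management of infusion reactions". Under grade 3, and again under grade 4, one bullet reads "No further treatment with nanoliposomal irinotecan will be permitted".

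Section 5.2 counts as dose limiting, in the first two cycles, "Grade 3 or 4 treatment related non-hematologic toxicities excluding alopecia". Its further qualifications concern grade 3 nausea, vomiting or diarrhea and electrolyte abnormalities. Infusion reactions are not excepted. On the consequence, 5.2 says that "when a patient experiences a DLT both drugs must be held and then both must be reduced". Resumption is allowed in 5.2, and again in 5.3, once the patient has recovered to grade 2 or less and the platelet and neutrophil thresholds are met.

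Section 5.3 applies the same action to a 5.2 toxicity at any time on treatment: the patient "will have a 1 dose level reduction of nanoliposomal irinotecan" and of temozolomide. Removal follows a second event ("Patients experiencing a second dose limiting toxicity will be removed from protocol treatment"), a need for more than one reduction, or a hold of more than 4 weeks for a DLT in cycles 1 or 2.

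**The concern.** The two parts of the protocol send the same patient in different directions. A site following 5.4 stops nanoliposomal irinotecan for good. A site following 5.2–5.3 holds it, reduces it and may give it again. No text says which prevails, and the stricter rule sits under an introduction that makes the whole list optional.

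This is a safety rule for an event that 5.4 defines, at grade 4, as life-threatening. Several sites take part and 5.4 lets each use its own policy, so practice could differ between sites with none of them in breach of the protocol.

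**Working it through.** There is no stated figure to reproduce. The check sets the rules side by side and then measures how far apart they are.

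**1. Do both rules cover the event?** Yes, if the reaction is treatment related. It then meets the non-hematologic criterion in 5.2 with no exception. In cycles 1–2 it is a DLT. After cycle 2 it is no longer called a DLT, but 5.2 and 5.3 still require the reduction of both drugs.

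**2. What does each rule require after a first event?**

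| | Sections 5.2–5.3 | Section 5.4 |
|---|---|---|
| Nanoliposomal irinotecan | Hold, reduce one level, may resume | No further dosing |
| Temozolomide | Hold, reduce to 25 mg/m²/day, may resume | Not addressed |
| Force of the text | Hold and reduction mandatory; resumption permitted | Prohibition, inside a list marked as not required |
| Reference to the other rule | None | None |

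**3. Does any other text settle precedence?**
- The administration text in 9.1.3 cites 5.4 only for lengthening the infusion. Otherwise it continues the drug until progression or withdrawal.
- Section 9.1.5 cites 5.4 for withholding the suspected drug and treating the reaction. It does not repeat the bar. It says that most patients with acute reactions to liposome drugs tolerate further infusions, without separating grades.
- Section 12.0 requires withdrawal for certain adverse events, but the investigator judges whether an event qualifies.

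None of these makes the stop mandatory.

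**4. Would the recovery test in 5.2–5.3 block re-exposure?** Probably not. Section 9.1.5 says these reactions generally resolve within 24 hours of stopping the infusion in most patients, though not by grade. The next dose is due at 14 days, so a patient could meet the criterion in time.

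**5. How far apart are the answers?** The inputs are the dose levels in 5.3: 80, 70, 50 and 43 mg/m². Under 5.3 the next dose as a share of the dose at reaction is the lower level divided by the current level:
- 70 / 80 = 87.5%
- 50 / 70 = 71.4%
- 43 / 50 = 86.0%

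Under 5.4 the next dose is 0 mg/m² in each case. These ratios measure the disagreement between the rules; they are not a risk estimate.

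**6. Who is affected?** Patients at level 1, 2 or 3 with no earlier reduction. At level −1 there is no lower level to use, and a patient already reduced once must be removed under 5.3.

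**The case against.** The best defense is that the intent is clear. Section 5.4 is the dedicated section for this event, and a specific rule normally overrides a general one. The bar is worded as a prohibition and appears twice. Where 5.4 means discretion it says so locally, as in "it is suggested but not required that you administer dexamethasone 10 mg IV". The optional label can be read as covering bedside care of the reaction only, leaving the later dosing decision binding. Resumption in 5.2–5.3 is also only permitted: "Patients can resume treatment post a dose limiting toxicity (with a dose level reduction to both drugs"), so a site that never rechallenges breaks neither rule on that point. Exclusion 3.2.12, which bars known hypersensitivity to the drug's components or other liposomal products, points the same way.

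Most of this stands as evidence of intent; the bar probably was meant to be mandatory. It does not repair the text. The optional label covers the whole list and names site policy as an alternative, while the hold and reduction in 5.2–5.3 are in mandatory wording. Exclusion 3.2.12 governs entry, not stopping.

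Other safeguards are real: withdrawal under section 12.0, including on the physician's view of the patient's best interest; SAE notification within 24 hours under 11.6; DSMB review under section 16.0; and removal after a second DLT. None automatically stops the drug after a first grade 3–4 reaction, and the second-DLT rule would act on a repeat reaction only after re-exposure.

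**Conclusion.** The inconsistency is real and should be corrected. After a first treatment-related grade 3–4 infusion reaction, the protocol both bars nanoliposomal irinotecan and provides for it at 71.4% to 87.5% of the previous dose, with no order of precedence.

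The practical effect is limited. Section 9.1.5 reports acute reactions in only a small number of patients on liposome drugs and gives no grade 3–4 rate, so the expected number of affected patients cannot be calculated. Many clinicians would stop the drug anyway. The event counts as a DLT in cycles 1–2 whichever rule governs later dosing, so the escalation decisions and the two-stage response design do not change.

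The conclusion assumes that the reaction is judged treatment related and that the patient has a lower dose level available with no earlier reduction.

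**What to change.** Move the grade 3–4 discontinuation out of the optional list in 5.4 and state it as a mandatory rule. The bedside steps can stay optional.

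In 5.2 and 5.3, add to the resumption and dose-reduction text: except grade 3–4 infusion reactions, after which nanoliposomal irinotecan is permanently discontinued (see 5.4).

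As a minor clarification, state whether temozolomide may continue alone in these patients, and at what dose. Section 9.2.1, which gives it until progression or withdrawal, suggests that it may continue, but 5.4 is silent.

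The cost is a short wording amendment to 5.2–5.4, with no effect on sample size, analysis or enrolment.
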